## **8. RESEARCH QUESTION AND OBJECTIVES**

To evaluate the effectiveness of add on therapy with Tiotropium Respimat® compared to increasing the dose of ICS in patients with a diagnosis of Asthma and on ICS/LABA therapy.

## **9. RESEARCH METHODS**

[figure not shown]
### **9.1 STUDY DESIGN**

Data extraction from both databases (I and II, see [section 9.4](#)) will be conducted by

. All patients will be required to have a prescription for ICS/LABA therapy [e.g. Advair (Diskus and HFA), Airduo, Breo, Dulera, or Symbicort]. The date of the first prescription of ICS/LABA within the study period (Jan 1st 2016 to Nov 30th 2018) will be defined as ICS/LABA-initiation (ICS/LABAi) date. This baseline cohort will then be followed to identify two cohorts (two arms of the study). One cohort that receives a prescription for Tiotropium Respimat® 1.25 mcg (on top of baseline ICS/LABA) will be classified as the ‘Tio’ group, and the second cohort that receives a “step-up” from baseline low-dose ICS/LABA to medium/high dose ICS/LABA or from baseline medium dose ICS/LABA to high dose ICS/LABA or an additional prescription/refill of high-dose-ICS/LABA following the first prescription of baseline high dose ICS/LABA within the study period, will be classified as the ‘NonTio’ group. The date of the first prescription for Tiotropium Respimat® 1.25 mcg in the ‘Tio’ group will be defined as the index date for the ‘Tio’ group. Similarly the date of the first prescription for a “step-up” from baseline low-dose ICS/LABA to medium/high dose ICS/LABA or from baseline medium dose ICS/LABA to high dose ICS/LABA or an additional prescription/refill of high-dose-ICS/LABA following the first prescription of baseline high dose ICS/LABA (evidenced by at least 90-days of prescription utilization) within the study period will be defined as the index date for the ‘NonTio’ group.

Patients will be required to have a minimum follow-up period of 30 days after the index date for the analyses of the primary endpoint with no limit on the maximum period (this 30-day minimum follow-up period requirement will be waived in a sensitivity analysis). Subject to sample size requirements, patients will be required to have available records for at least 12 months prior to the index date to ensure no prior use of Tiotropium Respimat® and to establish baseline patient characteristics. This 12-month period prior to the index date will be defined as the pre-index period.

Figure 9.1.1 Study Design

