#### 4. ABSTRACT

Name of company: Boehringer Ingelheim			
Name of finished medicinal product: Spiriva Respimat 1.25 mcg			
Name of active ingredient: Tiotropium Bromide® 1.25 mcg			
Protocol date: 18 Feb 2019	Study number: 0205-0543	Version/Revision: 1	Version/Revision date: NA
Title of study:	The effectiveness of Tiotropium Add-on therapy using a Real-world cohort of patients with Asthma		
Rationale and background:	While asthma imposes a substantial burden on the healthcare system, the cost of uncontrolled asthma is more than double that for controlled asthma patients. Asthma therapy involves a stepwise approach depending on control and severity levels. To better guide treatment decision making, it is imperative to understand the impact of different treatment choices on health outcomes in a real-world setting for patients taking ICS/LABA combinations.		
Research question and objectives:	To evaluate the effectiveness of add on therapy with Tiotropium Respimat® compared to increasing the dose of ICS in patients with a diagnosis of Asthma and on ICS/LABA therapy.		
Study design:	Retrospective cohort data analysis of patients with asthma prescribed with ICS/LABA therapy. Patients will be followed after the date of first ICS/LABA prescription and those prescribed Tiotropium Respimat® will be classified under the ‘Tio’ group while the rest will be under the ‘NonTio’ group. Outcomes will be compared between these two groups.		
Population:	Asthmatics 6 years and above and on ICS/LABA at baseline		
Variables:	Baseline measures will include patient demographics, medications, control status, comorbidities, resource use, eosinophil levels (if available), ACT score (if available).		
Data sources:	IMS Pharmedics (IMS or Database I); EMRClaims+ (Database II)		
Study size:	>6,300 (expected)		
Data analysis:	Propensity Score Matching will be conducted using baseline characteristics in order to ensure as much similarity between the two groups. Time to first exacerbation (primary outcome) will be compared between the two groups descriptively, as well as using Cox PH modelling techniques. Secondary outcomes will include rate of exacerbation, proportion of patients with exacerbation, health care resource use and cost during follow-up,		
Milestones:	Study protocol; Draft Results; Final Results		

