## **7. RATIONALE AND BACKGROUND**

While asthma imposes a substantial burden on the healthcare system, the cost of uncontrolled asthma is more than double that for controlled asthma patients (ACAAI). The European National Health and Wellness Survey ([P19-00715](#)) and the Real-world Evaluation of Asthma Control and Treatment (US) ([R16-0701](#)) survey both found that 55% of asthma patients were uncontrolled, even among those who are treated. Asthma therapy involves a stepwise approach depending on control and severity levels. Uncontrolled asthma, which may present regardless of severity level, results in exacerbations, use of systemic corticosteroids, and declined lung function ([P14-03600](#)). When asthma is not controlled, guidelines recommend increased ICS dose, and use of ICS in combination with long-acting  $\beta$ 2-agonists (LABA), and/or other add-on therapy, including leukotriene receptor antagonists (LTRA), antibody biologics or oral corticosteroids. The ERS/ATS guidelines ([P14-03600](#)) define severe asthma as that which remains uncontrolled despite use of high dose ICS as well as controller medications or systemic corticosteroids. Uncontrolled asthma is associated with an increased risk of exacerbation, which results in impaired lung function, reduced patient quality of life and increased health care resource use. To better guide treatment decision making, it is imperative to understand the impact of different treatment choices on health outcomes in a real-world setting for patients taking ICS/LABA combinations.

The intended audience will be health systems, payers and prescribers. The results of the study will be used to provide evidence of the effectiveness of tiotropium as add-on therapy in reducing exacerbations, reducing the increased dosing of current medications and health care resource utilization for their asthma patients.

In September 2015, the FDA approved Spiriva Respimat for Inhalation Spray for the long-term, once-daily, maintenance treatment of asthma in patients 12 years of age and older (6 years and above approved in Feb 2017).

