## 9.3 VARIABLES

### 9.3.1 Exposures

The exposure variables in this study include Tio initiation, and ICS/LABA dose increase or an additional prescription/refill of high-dose-ICS/LABA following the first prescription of baseline high dose ICS/LABA for at least 3 months.

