**Table 1: Matching Parameters**

Variable Name and Type	Description	Applicable to Study Cohort: 1=IMS, 2=EMRClaims+
ICS/LABA dose on ICS/LABAI date	The dose level of the first prescription on the ICS/LABAI date (low, medium, or high)	1 and 2
Demographics (categorical and continuous variables)	Age (10-year increments) and Gender Male/Female), Region (if available, Northeast, Midwest, South, West)	1 and 2
CCI (continuous variable)	Charlson Comorbidity Index score	1 and 2
Specific comorbidities (categorical variables)	Cardiovascular conditions, cerebrovascular diseases, hypertension, diabetes, metabolic and endocrine comorbidities, anxiety and depression, gastro-esophageal reflux disease, cancer and obesity identified using appropriate ICD codes. All above measures will be coded as binary (yes/no) variables.	1 and 2
Medications (categorical variable)	Polypharmacy level matched within a range of 2 drugs (for example, 0-2,3-5,6-8,8-10 and so on).	1 and 2
Asthma Control Status: Well Control or Poor Control (categorical variable)	‘Well Controlled’ if patient has no prescriptions for an OCS, and no asthma-related emergency department visits or hospitalizations other than the first diagnosis recorded in the data extracted (Ref: Stempel JACI 2005). Categories will include Well Controlled and Not Well Controlled.	1 and 2
Hospital admissions Outpatient visits ER visits and OCS use (categorical variables)	Poorly Controlled patients (“Not Well Controlled”) will further be matched based on the presence of asthma-related admissions, outpatient visits, and ER visits or use of OCS during the pre-index period.	1 and 2
Eosinophil levels (EMRClaims+ database only) (categorical variables)	Eosinophil level categories: <150 cells/μL, 151-300cells/μL, 301-400 cells/μL, ≥400 cells/μL (as available)	2
Asthma Control Test (ACT) results (EMRClaims+ database only) (categorical variables)	ACT score categories developed based on data distribution (as available)	2

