## **9.5 STUDY SIZE**

The expected number of asthma patients aged 12 years and above, without concurrent COPD, and continuous enrollment for 12 months prior to the Tiotropium Respimat® date is estimated to be approximately 2,100 to be matched to double (4200 patients) the number of NonTio patients resulting in a total N =6,300. Power calculation was conducted for the primary endpoint, time-to-first exacerbation by the end of the follow-up time. The calculation was based on detecting a significant treatment effect using Cox proportional hazard model. Estimates were obtained from the MEZZO trial comparing tiotropium 2.5 µg vs. salmeterol ([P15-01655](#)). Assuming 6.4% of patients in the control group followed

up for 5.5 months will have an exacerbation (based on the salmeterol group in the MEZZO study) and assuming a constant hazard rate, equating to an exponential rate parameter of 0.012 per month for the control group and 0.0096 per month for the Tio group, the power is calculated to be 77%. Using the Primo study, assuming 26.9% of patients in the control group followed up for 11 months will have an exacerbation (based on the Tio R 5 group in the 48-week study Primo) and assuming a constant hazard rate, equates to an exponential rate parameter of 0.028 per month in the control group and 0.0224 per month in the Tio group, the power is 98%. The Mezzo-derived power calculation likely underestimates the power since our study design includes sicker patients that required a step-up in ICS treatment (not required in the Mezzo Study). While we expect that the actual power will lie between the two estimates (assuming that the patient population is similar to the less severe Primo patients and the more severe MEZZO patients), the estimated power is greater than 77%.

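### The stated comparison is Tio versus an ICS dose increase, but NonTio also contains unchanged high-dose refills, and no planned analysis estimates the stated contrast

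*Combined protocol and SAP*

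**What the plan says.** The combined protocol and SAP describes the comparator in two ways.

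- **As a dose increase.** Section 8 evaluates Tio "compared to increasing the dose of ICS in patients with a diagnosis of Asthma and on ICS/LABA therapy". The abstract says the same: "compared to increasing the dose of ICS in patients with a diagnosis of Asthma". Section 9.7.1 glosses the key independent variable as Tio use against an ICS/LABA dose increase.
- **As a mixture.** Section 9.1 also admits "an additional prescription/refill of high-dose-ICS/LABA following the first prescription of baseline high dose ICS/LABA within the study period, will be classified as" NonTio. Section 9.3.1 gives the exposure as "ICS/LABA dose increase or an additional prescription/refill of high-dose-ICS/LABA following the first prescription of baseline high dose ICS/LABA for at least 3 months". Section 9.12 repeats the two-part requirement.

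The plan is open about part of this. Elsewhere in section 9.7.1 the comparison is simply Tio against NonTio. Section 9.9 says that including persistent high-dose users may make the results harder to interpret, because Tio patients whose asthma has worsened are matched to patients whose medication has not changed. Table 1 matches on the dose level (low, medium or high) at the first ICS/LABA prescription.

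The only sensitivity analysis named is in section 9.1: "this 30-day minimum follow-up period requirement will be waived in a sensitivity analysis". In arguing that power is probably understated, section 9.5 says that "our study design includes sicker patients that required a step-up in ICS treatment (not required in the Mezzo Study".

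**The concern.** Tio versus stepping up the dose and Tio versus staying on a high dose are different questions. A single hazard ratio averages them, with weights that depend on how many NonTio patients are refills, and the documents do not give that share. The pooled result therefore cannot by itself be read as the answer to section 8.

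This bears on use of the results. Section 7 says they will "provide evidence of the effectiveness of tiotropium as add-on therapy in reducing exacerbations" and names payers, prescribers and health systems as the audience, whereas section 9.9 rules out effectiveness claims. Whichever position prevails, a reader who sees the objective beside the pooled hazard ratio is likely to take the comparator to be a dose increase.

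**Working it through.** **1. Can the two components be told apart?** Under section 9.1 a NonTio patient who starts on low or medium dose can enter only by a step-up, and one who starts on high dose can enter only by a further high-dose prescription. Within NonTio, baseline dose therefore identifies the component exactly, and Table 1 already holds it.

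**2. Does anything planned separate them?**

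- Matching: baseline dose is one input to a propensity score. Score matching within a caliper does not force agreement on dose within a matched set, and even perfect balance gives one hazard ratio.
- Section 9.12 intends Tio patients with an ICS increase to be matched on increased dose or additional prescription, but Table 1 lists no such variable.
- Covariate adjustment: section 9.7.1 adds unbalanced characteristics to the regression. This also gives one hazard ratio.
- Baseline tables would show the share at each dose, but no effect estimate.
- Sensitivity analysis: the one named concerns the 30-day rule. The sub-group analyses mentioned in section 9.9 relate to Database II lung-function and ACT data.

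**3. Effect on the pooled hazard ratio.** This is illustration only. Assume the same Tio hazard throughout, a hazard ratio of 0.80 against step-up and r against refill, and a refill share f. The pooled hazard ratio is then 1/[(1−f)/0.80 + f/r]. At f = 0.5:

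- r = 0.70: 1/(0.625 + 0.714) = 0.75
- r = 0.80: 1/(0.625 + 0.625) = 0.80
- r = 1.00: 1/(0.625 + 0.500) = 0.89

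The result can fall on either side of 0.80 or not move. The documents give neither f nor r.

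**4. Reproducing the plan's power.** Inputs from section 9.5: 2,100 Tio and 4,200 NonTio; rates of 0.012 versus 0.0096 and 0.028 versus 0.0224 per month. The hazard ratio is 0.0096/0.012 = 0.0224/0.028 = 0.80. Rate check: −ln(1−0.064)/5.5 = 0.0120 and −ln(1−0.269)/11 = 0.0285, against the plan's 0.012 and 0.028.

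Assumptions, since the plan states neither: two-sided alpha of 0.05 and a common follow-up T of 10 months. Ten months was chosen because it reproduces both stated powers; 5.5 months gives only 53% for the first.

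Expected events d = 4,200(1−e^(−λc·T)) + 2,100(1−e^(−λt·T)), and SE(ln HR) = √[1/(d × 1/3 × 2/3)] (Schoenfeld).

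- 0.012 per month: d = 475 + 192 = 667, power 77.5% (plan: 77%).
- 0.028 per month: d = 1,026 + 421 = 1,447, power 97.9% (plan: 98%).

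**5. Precision of a low/medium estimate.** Multiply d by an assumed step-up share of the matched sets. At 50% and 0.012 per month, d = 334, SE = 0.116, and 0.80 × exp(±1.96 × 0.116) = 0.64 to 1.00.

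| Step-up share | d (0.012) | 95% CI | Power | d (0.028) | 95% CI | Power |
|---|---|---|---|---|---|---|
| 100% | 667 | 0.68–0.94 | 77.5% | 1,447 | 0.72–0.89 | 97.9% |
| 75% | 500 | 0.66–0.96 | 65.3% | 1,085 | 0.71–0.91 | 93.4% |
| 50% | 334 | 0.64–1.00 | 48.5% | 724 | 0.69–0.93 | 80.8% |
| 25% | 167 | 0.58–1.10 | 27.4% | 362 | 0.64–1.00 | 51.6% |

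Unrounded, the upper limit is just above 1 at 50% and 0.012 per month, and just below 1 at 25% and 0.028 per month. At a 50% share, moving T from 8 to 12 months moves power from 40.8% to 55.3%, or from 72.7% to 86.5%.

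The ratio of the two stratum hazard ratios at a 50% share has SE = √2 × the half-sample SE. Its 95% interval around 1 is 0.725 to 1.380, or 0.804 to 1.244, which is too wide to serve as a test.

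These figures treat matched sets as pure by dose, which the planned matching does not guarantee. They describe the precision of the added estimate, not bias in the pooled one.

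**The case against.** The mixture is an explicit definition, disclosed as a limitation. It is also coherent: under the plan's dose categories a patient already on high dose has no higher category to move to, so stepping up, or continuing if already high, can be seen as one comparator strategy. That stands, and it is why the pooled analysis can remain primary. It does not make the wording of the objective fit, and it supplies no estimate for the contrast named there.

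Two objections to stratifying also stand. Within NonTio, comparator type coincides completely with baseline dose, so a difference between strata may reflect dose or severity and not comparator type. And section 9.12 says some Tio patients have an ICS increase at or before their Tio prescription, so the low/medium stratum may mix Tio alone and Tio plus an increase against an increase. The estimates must be labelled accordingly.

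A reader might infer that the refill patients bias the hazard ratio in a known direction, or that the study is invalid. The documents do not support either: they give no refill share and no effect for either component, and the two contrasts may agree. A reader might equally infer that the stratified estimates would isolate the effect of comparator type. For the reasons just given, they would not.

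**Conclusion.** The point holds as a mismatch between the stated comparison and the defined comparator, with no planned estimate of the former. It rests on the text of sections 4, 8, 9.1, 9.3.1, 9.7.1 and 9.12 and not on a calculation. Disclosure in section 9.9 and matching on baseline dose reduce the problem but leave one pooled hazard ratio. The step-up argument for higher power in section 9.5 does not apply to the refill patients. The effect on the pooled hazard ratio is unknown in size and direction and may be nil. The precision figures depend on an assumed step-up share, a hazard ratio of 0.80 and an assumed 10 months of follow-up. This should be corrected before analysis; it does not invalidate the design. The study design figure was not available to check.

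**What to change.** Keep the matching and the pooled Cox analysis as planned, and make these changes:

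1. In the abstract, section 8 and section 9.7.1, name the comparator as step-up or continued high-dose ICS/LABA.
2. In section 9.5, limit the step-up reasoning to step-up patients.
3. Report the step-up and refill shares of NonTio.
4. In section 9.7.1, pre-specify supportive hazard ratios with confidence intervals for low/medium and for high baseline dose, with covariate balance reported within each stratum.
5. Require any statement about Tio versus a dose increase to rest on the low/medium estimate and its interval, not on the pooled hazard ratio.
6. State both limits beside these estimates: strata may differ because of baseline dose or severity, and some low/medium Tio patients may have had an ICS increase at or before index. Report that last share.

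I would not rematch within dose strata, since that could change the primary sample and lose an unknown number of patients.

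The cost is wording in four sections and one supportive analysis on a variable already in Table 1, plus a count of Tio patients with an ICS increase from the prescription records. The primary analysis and its power are unchanged. The price is a less precise low/medium estimate, as tabulated above.

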## **9.9 LIMITATIONS OF THE RESEARCH METHODS**

Claims and EMR data are subject to certain limitations. The presence of a claim for a filled prescription or prescription absent a claim does not indicate that the medication was consumed or that it was taken as prescribed, and any medications filled over-the-counter or provided as samples by the physician will not be observed in the claims data. Finally, as with all claims-based analyses, study results may not be generalizable to the overall population as patients who have commercial health insurance may be different from those with non-commercial or without (commercial) health insurance. Database I underrepresents the population aged 65 years and older, which may affect external validity in the case of Medicare, Medicare Advantage or Medicaid patients. Since unmatched patients will be excluded, the results may not be generalizable to all patients. Some study measures and outcomes will include missing data and hence reduce the sample size. Not all patients in Database II will have lung function results or ACT scores, therefore, the sample size for related secondary endpoints or sub-group analyses may produce results for these analyses that are not generalizable. While duplication analyses will make double counting the same patient across both datasets negligible, it should be noted that the same patient may be present in both cohorts.

Including patients with persistent use of high-dose ICS/LABA (as opposed to an increase in ICS/LABA dose) in the NonTio group, may complicate the interpretation of the results, as patients with a deterioration in their asthma necessitating an increase in asthma medication (Tio group) will be matched to patients continuing on the same medication (high-dose ICS/LABA).

No claims regarding the effectiveness of Tio should be made on the basis of this study. This real-world evidence study lacks controls available with randomized controlled trials. Patient misclassification, missing data, objective and reliable measurement of patient outcomes, and lack of detailed information regarding subjects' clinical history or clinical status during the study timeframe may undermine the accuracy of our study results.

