## 9.12 BIAS

### Channeling Bias Mitigation

Introduction of channeling bias in this study is highly likely using retrospective claims data based on asthma medication use; patients between the two cohorts may differ in baseline control and severity levels. On aggregate, patients for whom Tiotropium Respimat® 1.25 mcg was added (vs NonTio) are likely to be less well-controlled and more severe both at baseline and during the follow up period. Absent a method to control for this channeling bias, it is likely that placing sicker patients in the Tiotropium Respimat® 1.25mcg group will confound an accurate comparison of cost, resource use, and other outcomes between the groups. Two design features of our study will help mitigate this bias. First, our comparison (NonTio) group will be required to step-up their baseline ICS/LABA dose or have an additional prescription/refill of high-dose-ICS/LABA following the first prescription of baseline high dose ICS/LABA within the study period. Second, we will use Propensity Score Matching (PSM) to match patients on key measures of disease control and severity as listed in [Table 1](#), such as demographics, Charlson Comorbidity Index (CCI) score, specific comorbidities, number of prescriptions (overall and asthma-related medications). This baseline matching strategy will be particularly important to ensure that patients in the TIO group who have a corresponding increase in their ICS dose at or prior to the date of their TIO prescription (for example, if the patient has an exacerbation), will be matched to a corresponding NonTIO patient in terms of increased ICS dose or additional ICS prescription. It should be noted that after the prescription index date for both Tio and NonTio patients, we anticipate changes in ICS medication for patients in both cohorts. These ICS medication changes reflect patient

outcomes in the follow-up period, where patients who encounter exacerbation in either group are likely to see a change in the ICS dose.

As a result, post-index period ICS medication changes will not alter the classification of patient groups nor will it be the basis for exclusion of these patients.

We will conduct 1:2 matching using a nearest neighbour matching approach with a radius of  $0.2 * SD(\log(P))$ . This will be conducted in both databases (IMS: Cohort I and EMRClaims+: Cohort II) separately.

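### NonTio entry carries a 90-day prescription condition with no stated start and Tio entry has none; if the 90 days run past the index date, controls are selected on time at risk

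*Combined protocol and SAP*

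**What the plan says.** Section 9.1 dates Tio entry at the first tiotropium prescription and sets no duration. It dates NonTio entry at the first step-up in ICS/LABA dose or, for patients already on high dose, the first additional high-dose refill. That index-date sentence then adds "evidenced by at least 90-days of prescription utilization".

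Other places differ:

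- The classification sentence in section 9.1 places a patient with an additional high-dose refill "following the first prescription of baseline high dose ICS/LABA within the study period, will be classified as the ‘NonTio’ group", with no 90-day condition.
- Section 9.3.1 describes the refill route as a refill "following the first prescription of baseline high dose ICS/LABA for at least 3 months".
- Section 9.9 speaks of "Including patients with persistent use of high-dose ICS/LABA (as opposed to an increase in ICS/LABA dose) in the NonTio group".
- Section 9.12 says "our comparison (NonTio) group will be required to step-up their baseline ICS/LABA dose or have an additional prescription/refill of high-dose-ICS/LABA", again without the 90 days. It also says that "post-index period ICS medication changes will not alter the classification of patient groups nor will it be the basis for exclusion of these patients".
- The minimum follow-up of 30 days applies to both groups, "with no limit on the maximum period (this 30-day minimum follow-up period requirement will be waived in a sensitivity analysis").

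On patients who meet both definitions, the abstract says that those prescribed tiotropium "will be classified under the ‘Tio’ group while the rest will be under the ‘NonTio’ group". Section 9.12 describes Tio patients whose ICS dose rose at or before their tiotropium date. Section 9.1 gives no rule for them.

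**The concern.** A cohort comparison from time zero needs group membership to be settled at time zero. If the 90 days extend past the index date, a control is kept only if refills continue during the period in which primary events are counted. A Tio patient is kept whatever happens after the first prescription. Matching on the pre-index covariates of Table 1 cannot repair selection on later behaviour. Waiving the 30-day minimum follow-up does not test it either, because that minimum applies to both groups and is shorter than 90 days.

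The primary hazard ratio is at stake. It is biased against Tio if controls with early exacerbations fail the condition more often, and in favour of Tio if controls without them do. Two programmers could build different control groups from the present wording.

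**Working it through.** **1. When can the 90 days be complete?** For the refill route, index is the first additional refill. Count from the first in-period high-dose prescription, assuming the refill falls when supply runs out:

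- 30-day fill: 30 days accrued at index, 90 − 30 = 60 fall after it.
- 60-day fill: 90 − 60 = 30 days fall after it.
- 90-day fill: none fall after it.

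Counted from the index fill, up to 90 days fall after index, unless a 90-day supply dispensed that day is enough. If step-up is covered and the condition means use at the new dose, all of it falls after index, because that dose starts there. The 90 days are complete by index only with a 90-day first fill, with use counted from before the first in-period prescription, or with index moved to a later refill. The text states none of these.

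**2. Inputs (section 9.5).** 2,100 Tio and 4,200 NonTio; control hazards 0.012 and 0.028 per month; Tio hazards 0.0096 and 0.0224. The hazard ratio is 0.0096/0.012 = 0.0224/0.028 = 0.80.

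**3. Reproducing the plan's figures.** −ln(1 − 0.064)/5.5 = 0.0120 and −ln(1 − 0.269)/11 = 0.0285, close to the stated rates. With Freedman's formula, 1:2 allocation and two-sided 5% (assumed), 11 months in both scenarios gives power 77.9% and 98.0%, against 77% and 98% stated. The lower-rate scenario gives only 50.0% at 5.5 months. I therefore use 11 months for both; the plan sets no maximum follow-up.

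**4. Events and precision at 11 months.**

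- Lower rate: 2,100(1 − e^(−0.0096×11)) + 4,200(1 − e^(−0.012×11)) = 210 + 519 = 730 (rounded total).
- Higher rate: 459 + 1,113 = 1,572.
- SE of log HR = √(1/e₁ + 1/e₀) = 0.082 and 0.0555.
- Share of NonTio first events in the first 3 months, (1 − e^(−3h))/(1 − e^(−11h)): 28.6% and 30.4%.

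**5. Effect on the Cox estimate.** This is the large-sample limit of the one-covariate Cox model with exponential times, 1:2 allocation, true HR 0.80 and a 3-month post-index window. The drop-out and the share of NonTio under the rule are assumptions. Values are for the lower / higher rate.

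| Share of NonTio affected | 25% of early-event controls lost | 25% of the other controls lost | 25% of both lost |
|---|---|---|---|
| A quarter | 0.814 / 0.815 | 0.785 / 0.785 | 0.800 / 0.800 |
| Half | 0.829 / 0.830 | 0.769 / 0.769 | 0.800 / 0.800 |
| All | 0.860 / 0.862 | 0.732 / 0.731 | 0.800 / 0.800 |

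**6. Hand check (lower rate).** Drop-out multiplies the early NonTio hazard by about k, or by 1/k in the other direction, so log HR ≈ ln 0.80 ± 0.285 × ln(1/k).

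- All affected, k = 0.75: −0.2231 ± 0.0820, giving 0.87 and 0.74.
- A quarter affected, k = 1 − 0.25 × 0.25 = 0.9375: −0.2231 ± 0.0184, giving 0.815 and 0.785.

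Both are close to the table.

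**7. Scale.** With all affected, ln(0.860/0.80) = 0.072 and ln(0.732/0.80) = −0.089, or 0.9 and 1.1 SE at the lower rate; at the higher rate the shifts are 1.3 and 1.6 SE. With a quarter affected the shifts are 0.2 to 0.3 SE.

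**8. Other windows and follow-up (all affected).** A 2-month window gives 0.84 and 0.75; a 1-month window gives 0.82 and 0.77 to 0.78. With a 3-month window, 18 months of follow-up (assumed) gives 0.84 and 0.75 to 0.76; 5.5 months gives 0.93 and 0.68, but at the lower rate with only 376 events (SE 0.114).

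**9. Cost of a day-90 start in both groups.** Events before day 90 number 208 and 475, so 730 − 208 = 522 (28.5% lost) and 1,572 − 475 = 1,097 (30.2% lost). If 25% of each group also fail the condition, 0.75 × 522 ≈ 391 and 0.75 × 1,097 ≈ 823 remain, a loss of 46% and 48%.

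**The case against.** The strongest reply is that the protocol intends the 90 days as baseline use completed before index. The parenthesis directly follows the words about baseline high-dose use, section 9.3.1 can be read the same way, section 9.9 describes patients continuing on the same medication, and section 9.12 rules out exclusion for later ICS changes. This is a fair reading, and under it no post-index selection exists. It does not close the matter: the stated index is the first additional refill, and step 1 shows that the reading then needs a fill length, earlier use or a later index that the text does not give. The study design figure may mark the window, so the gap is established for the text only.

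The second reply concerns size. Section 9.3.1 ties the 3 months to the refill route, so the all-affected figures are an outer case. Drop-out, its link to exacerbation, route shares and fill lengths are all absent from the documents. This stands. The hazard ratios illustrate a mechanism and do not predict the result.

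A reader might infer that the design is biased as it stands, that the bias favours tiotropium, or that controls are guaranteed 90 event-free days. The documents support none of these. The bias depends on the reading, its direction is unknown and can be nil, and an exacerbation does not end observation or by itself remove a control.

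**Conclusion.** The point holds conditionally. The 90-day condition sits on the NonTio side only, its start and scope are not stated in the text, and the descriptions of NonTio entry disagree on whether it applies. Counted from the first in-period high-dose prescription with 30- or 60-day fills, it selects controls on post-index refills, against section 9.12.

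If that is how it is applied, an assumed 25% differential drop-out moves a true hazard ratio of 0.80 to between 0.785 and 0.81 when a quarter of controls are affected, and to between 0.73 and 0.86 when all are, at 11 months. The first is small beside the standard error and the second is comparable to it. Confidence is medium, because the intended reading may be the harmless one. The wording should still be settled before the cohorts are built.

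A secondary gap is of the same kind. The abstract and section 9.12 imply that a patient who steps up and later starts tiotropium is placed in Tio. Remaining in NonTio may then depend on tiotropium use after the NonTio index date.

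**What to change.** 1. **Primary analysis.** Define NonTio entry only from information available on or before the index date. Either drop the 90-day condition or, for the refill route only, require it to be complete by the index refill. For step-up patients, set no condition on later use of the new dose.
2. **Wording.** Reconcile sections 9.1, 9.3.1 and 9.12 on when the 90 days start and which routes they cover.
3. **One sensitivity analysis.** Apply the same 90-day condition to both groups and start follow-up at day 90. Given the event losses in step 9, it should not be the primary analysis.
4. **Patients meeting both definitions.** Reconcile the abstract with sections 9.1 and 9.12. Do not remove a patient already indexed as NonTio because of later tiotropium. Report results with and without censoring at tiotropium start, since that censoring may be informative.

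The cost is protocol wording and programming on data already being extracted. Without the condition, some NonTio patients will have short exposure. If it must be complete by index, refill-route index dates move later and fewer patients are eligible.
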